#### 8.3.5 ADVERSE EVENT REPORTING

In consultation with the PI, a trained member of the study team will be responsible for conducting an evaluation of an adverse event and shall report the results of such evaluation to the NIH and the reviewing Institutional Review Board (IRB) as soon as possible, but in no event later than within 24 hours after the investigator first learns of the event.

#### 8.3.6 SERIOUS ADVERSE EVENT REPORTING

In consultation with the PI, a trained member of the study team will be responsible for conducting an evaluation of a serious adverse event and shall report the results of such evaluation to the NIH and the reviewing Institutional Review Board (IRB) as soon as possible, but in no event later than within 24 hours after the investigator first learns of the event.

#### 8.3.7 REPORTING EVENTS TO PARTICIPANTS

*The PI will be responsible for reporting AEs or SAEs related to the study to participants as soon as possible, but in no event later than within 24 hours after the investigator first learns of the event.*

*For incidental findings from MRI brain scan, the MRI facility will inform the PI if there is incidental finding and the PI will report the finding to participants as soon as possible, but in no event later than within 24 hours after the investigator first learns of the event.*

---

### 8.3.8 EVENTS OF SPECIAL INTEREST

N/A

---

### 8.3.9 REPORTING OF PREGNANCY

N/A

## 8.4 UNANTICIPATED PROBLEMS

---

### 8.4.1 DEFINITION OF UNANTICIPATED PROBLEMS

This protocol uses the definition of Unanticipated Problems as defined by the Office for Human Research Protections (OHRP). OHRP considers unanticipated problems involving risks to participants or others to include, in general, any incident, experience, or outcome that meets all of the following criteria:

- Unexpected in terms of nature, severity, or frequency given (a) the research procedures that are described in the protocol-related documents, such as the Institutional Review Board (IRB)-approved research protocol and informed consent document; and (b) the characteristics of the participant population being studied;
- Related or possibly related to participation in the research (“possibly related” means there is a reasonable possibility that the incident, experience, or outcome may have been caused by the procedures involved in the research); and
- Suggests that the research places participants or others at a greater risk of harm (including physical, psychological, economic, or social harm) than was previously known or recognized.

---

### 8.4.2 UNANTICIPATED PROBLEMS REPORTING

The investigator will report unanticipated problems (UPs) to the reviewing Institutional Review Board (IRB) and to the Data Coordinating Center (DCC)/lead principal investigator (PI). The UP report will include the following information:

- Protocol identifying information: protocol title and number, PI's name, and the IRB project number
- A detailed description of the event, incident, experience, or outcome
- An explanation of the basis for determining that the event, incident, experience, or outcome represents an UP
- A description of any changes to the protocol or other corrective actions that have been taken or are proposed in response to the UP

To satisfy the requirement for prompt reporting, UPs will be reported using the following timeline:

- UPs that are serious adverse events (SAEs) will be reported to the IRB and to the DCC/study sponsor/funding agency within 10 business days of the investigator becoming aware of the event.
- Any other UP will be reported to the IRB and to the DCC/study sponsor/funding agency within 10 business days of the investigator becoming aware of the problem
- All UPs should be reported to appropriate institutional officials (as required by an institution's written reporting procedures), the supporting agency head (or designee), and the Office for Human Research Protections (OHRP) within 10 business days of the IRB's receipt of the report of the problem from the investigator.

#### 8.4.3 REPORTING UNANTICIPATED PROBLEMS TO PARTICIPANTS

*The PI will be responsible for reporting UPs related to the study to participants as soon as possible, but in no event later than 10 working days after the investigator first learns of the UP.*

### 9 STATISTICAL CONSIDERATIONS

#### 9.1 STATISTICAL HYPOTHESES

- Primary Endpoint(s):

We hypothesize that, compared to participants who receive a RT control intervention, participants who receive IBMT for improving brain outcomes will have improved anterior cingulate cortex/medial prefrontal cortex functional activity after completing the intervention at post-assessment. Alternatively, our null hypothesis is that there will be no difference in the effects of IBMT for improving brain outcomes and those of RT at post-assessment.

#### 9.2 SAMPLE SIZE DETERMINATION

*Our RCT design is focused on determining if within-person brain changes significantly differ across the intervention groups. All participants in this study will be those who use polysubstance. In prior work involving smokers (N = 27), we detected significant fMRI signal changes in the ACC/mPFC (Cohen's  $d = .90$ ) after 2-wk of IBMT than before IBMT . Compensating for the expected variability of findings in ACC/mPFC activity in polysubstance use, we thus expect a conservative, medium to large (Cohen's  $d = .80$ ) effect (i.e., we expect the effect size between the intervention and control conditions to be 0.80 at post-intervention) based on ours and other studies. However, we may expect polysubstance users to be somewhat more variable. Given the power considerations, we increased our sample size to 35 per group, which will give us 90% power to detect fMRI signal changes evoked by IBMT. The target sample size for the proposed study in the R61 phase (n = 70; 35/condition) is designed to provide sufficient evidence to detect significant brain changes in ATC users following interventions. Given we anticipate up to 20% attrition across the R61 phase of the study, power analysis suggests adequate power.*

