### 9.4.2 ANALYSIS OF THE PRIMARY ENDPOINT(S)

*The primary endpoints are brain assessments and are all repeated measures assessed at baseline and post-intervention. For brain assessment of brain assessment of functional activity, whole-brain analyses of fMRI timeseries during resting state will be calculated and for all endpoints based on standardized processing pipelines of fMRI data using REST software ([www.restfmri.net](http://www.restfmri.net)). After these data preprocessing and calculation, numerical values will be generated for each brain voxel. Next, the effects of intervention (IBMT vs. RT) on primary endpoints will be examined using repeated-measures ANOVA with time x group interaction effect. Threshold-free cluster enhancement approach will be used to identify clusters showing significant effects. Variance and covariance across repeated measures will be calculated as part of the ANOVA. Age and sex will be included as covariates to control for potential confounding effects of age and sex on brain outcomes. Results will be presented as F values for the interaction effect, along with p values to indicate statistical significance. Normality and homogeneity of variance assumptions will be checked using SPSS built-in tools for ANOVA. Multiple comparison corrections will be conducted using FDR correction. Missing data will be handled with case-wise deletion.*

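### Adjusting for the baseline scan would be more precise than the planned time x group test, and the 90% in Section 9.2 holds only with 35 analysed per arm on unstated assumptions

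*Combined protocol and SAP*

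**What the plan says.** Section 9.2 sets the aim as a comparison of change: "Our RCT design is focused on determining if within-person brain changes significantly differ across the intervention groups". The one figure it gives from prior work is d = 0.90 in 27 smokers, for signal "after 2-wk of IBMT than before IBMT", which is a before-after effect within IBMT. It lowers this to 0.80, also citing other studies without figures, and restates it as a between-arm effect: "we expect the effect size between the intervention and control conditions to be 0.80 at post-intervention". It then fixes 35 per group, "which will give us 90% power to detect fMRI signal changes evoked by IBMT", and calls power adequate with up to 20% attrition without giving a figure after attrition.

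Section 9.1 states the null as "there will be no difference in the effects of IBMT for improving brain outcomes and those of RT at post-assessment". In Section 9.4.2 the effect of IBMT versus RT "will be examined using repeated-measures ANOVA with time x group interaction effect", and "Age and sex will be included as covariates to control for potential confounding effects of age and sex on brain outcomes". The baseline brain value is not a covariate. The analysis is whole-brain: "Threshold-free cluster enhancement approach will be used to identify clusters showing significant effects", with FDR correction and case-wise deletion.

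Section 9.3 analyses only those who had all 10 sessions and have complete primary data. Section 5.5 expects 56 of the 70 recruited to complete. Section 9.4.1 adds that the approach is well powered for smaller effects too, with no calculation.

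**The concern.** With two scans, the time x group interaction is the between-arm difference in mean change. That is a valid comparison under randomisation, but it uses the baseline scan inefficiently. Subtracting the baseline in full carries its noise into the outcome, whereas regressing on it removes only what it predicts. The scan is already scheduled for everyone, so the lost precision buys nothing.

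The second issue is what the 90% refers to. If 0.80 is in SDs of change, it applies directly to the planned test. If it is in SDs of the post-intervention value, the power of that test depends on r. Section 9.2 names neither the SD nor r, and the wording points both ways. The calculation also matches 35 per arm, although the plan expects to analyse about 28.

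At stake is the precision and interpretability of an R61 result that Section 9.4.1 places ahead of the full-scale R33 trials.

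**Working it through.** **Inputs from the documents.** d = 0.80, 35 per arm and 90% power (9.2); 56 completers (5.5), so 56/2 = 28 per arm if losses are even; time x group test with age and sex (9.4.2).

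**Assumed, because the documents do not give them.** Two-sided 5%; equal SDs at both scans and in both arms; one mean ACC/mPFC value per scan; r from 0.2 to 0.7. Power is from the noncentral t distribution.

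**1. The stated 90%.** A two-sample t test with d = 0.80 has 91.0% at 35 per arm (normal approximation 91.7%), so the figure reproduces. At 28 per arm it has 83.6% (84.9%), so it does not.

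**2. Error variances.** Let the SD at each scan be s.
- Change: 2s²(1−r).
- Post-intervention value adjusted for baseline: s²(1−r²).
- Ratio: (1−r²)/[2(1−r)] = (1+r)/2, which is 0.65, 0.75 and 0.85 at r = 0.3, 0.5 and 0.7.

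The ratio does not depend on which SD defines 0.80. Dividing 35 by it gives about 54, 47 and 41: ANCOVA with 35 per arm is as precise as the interaction with those numbers. From 28 per arm the equivalents are about 43, 37 and 33.

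**3. Effective d for each test.**
- 0.80 in post-intervention SDs: interaction 0.80/√[2(1−r)]; ANCOVA 0.80/√(1−r²).
- 0.80 in change SDs: interaction 0.80 at any r; ANCOVA 0.80·√[2/(1+r)].

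Example at r = 0.3: post-intervention SDs give 0.676 and 0.839; change SDs give 0.80 and 0.992.

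**4. Power (%).** ANCOVA is charged one extra degree of freedom. Including age and sex in both models moves these by no more than about 0.1 point.

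| Per arm | SD behind 0.80 | Test | r = 0.2 | 0.3 | 0.4 | 0.5 | 0.7 |
|---|---|---|---|---|---|---|---|
| 35 | post | interaction | 74.2 | 79.6 | 85.4 | 91.0 | 98.9 |
| 35 | post | ANCOVA | 92.0 | 93.3 | 94.9 | 96.8 | 99.6 |
| 35 | change | interaction | 91.0 | 91.0 | 91.0 | 91.0 | 91.0 |
| 35 | change | ANCOVA | 98.9 | 98.3 | 97.6 | 96.8 | 94.7 |
| 28 | post | interaction | 64.2 | 70.0 | 76.5 | 83.6 | 96.7 |
| 28 | post | ANCOVA | 85.1 | 86.9 | 89.4 | 92.4 | 98.4 |
| 28 | change | interaction | 83.6 | 83.6 | 83.6 | 83.6 | 83.6 |
| 28 | change | ANCOVA | 96.7 | 95.4 | 94.0 | 92.4 | 89.0 |

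**5. Thresholds for 90%.** At 35 per arm the required d is 0.786, so on the post-intervention-SD reading the interaction needs r of at least 1 − (0.80/0.786)²/2 = 0.48. At 28 per arm it needs about 0.59. ANCOVA at 28 per arm reaches 90% on both readings only for r between about 0.42 and 0.64. Its lowest value is about 84%, near r = 0 on the post-intervention-SD reading; on the change-SD reading it falls towards the same value as r rises (85.4% at r = 0.9).

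**6. Smaller effects (9.4.1).** At r = 0.5, where the readings coincide, and 35 per arm, d = 0.7, 0.6 and 0.5 give the interaction 82%, 70% and 54%, and ANCOVA 92%, 82% and 66%. The answer depends on r: at r = 0.7 on the post-intervention-SD reading the interaction has 96% at d = 0.7 and 89% at d = 0.6.

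**The case against.** The planned test is legitimate, and no error in 9.4.2 is shown. Section 9.2 speaks of within-person change and signal change, so its mention of post-intervention may only name the time point. On that reading the 90% matches the planned interaction at 35 per arm whatever r is. The null in 9.1 fits a comparison of change as well as one of final values. All of this stands, so preferring ANCOVA is an argument about efficiency, not validity.

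A reader might infer that the trial is underpowered. The documents do not support that: the shortfall depends on an unstated SD, an unstated r and the number finally analysed. A reader might equally infer that baseline adjustment secures 90% on either reading. That is so with 35 analysed per arm, but not with 28.

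It is also true that every figure here is for a single regional mean, while 9.4.2 plans a corrected whole-brain map. Power for that map will be lower and cannot be computed from the documents. Finally, whether 0.80 already reflects results against RT depends on cited studies that are not available here, so no claim is made that 0.80 is too large.

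What remains is the variance ratio, which holds on both readings, and a power statement that fits neither the expected analysis set nor a named scale.

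**Conclusion.** The point holds as a cheap improvement. Baseline adjustment cuts the error variance to (1+r)/2 of that of the planned test, a reduction of 35%, 25% and 15% at r = 0.3, 0.5 and 0.7. The stated 90% reproduces only with 35 analysed per arm and, for the planned interaction, only if 0.80 is in change SDs or r is about 0.48 or more. At the 28 per arm the plan expects to analyse, ANCOVA exceeds the interaction on both readings in every column of the table, by up to about 21 points (r = 0.2, post-intervention SDs), yet does not assure 90%.

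This rests on two-sided 5%, equal SDs, even losses between arms and one mean ACC/mPFC value. Neither test removes any selection introduced by analysing completers only, which is a separate matter.

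**What to change.** - **9.4.2:** Make the primary model an ANCOVA of post-intervention ACC/mPFC activity on arm, its baseline value, age and sex, and report the adjusted difference with a 95% CI. In the whole-brain map the covariate is the voxelwise baseline image; otherwise use the mean of a region defined in advance. Keep the time x group ANOVA as supportive.
- **9.2:** Name the SD behind 0.80 and restate power for the ANCOVA at 28 and 35 per arm over a range of r. Say that the figures are for a single mean ACC/mPFC value and that whole-brain corrected power will be lower.
- **9.4.1:** Delete the claim about smaller effect sizes, or support it with figures.

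**Cost:** one degree of freedom, with no new scans, visits or participants. The voxelwise covariate adds processing work. Choosing the regional mean instead changes the primary analysis from a map to a region, which must be fixed beforehand. The single 90% becomes a range.

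### The 90% power in section 9.2 is the power at d = 0.80 with all 70 participants evaluable; it covers neither the further variability the section raises nor the planned 20% attrition

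*Combined protocol and SAP*

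**What the plan says.** Section 9.2 (Sample Size Determination) builds the sample size in this order.

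- It cites a pre-to-post effect of d = 0.90 in 27 smokers.
- It lowers this for the present population: "Compensating for the expected variability of findings in ACC/mPFC activity in polysubstance use, we thus expect a conservative, medium to large" effect of d = 0.80, which it defines as a between-arm quantity: "we expect the effect size between the intervention and control conditions to be 0.80 at post-intervention".
- It then raises variability again: "However, we may expect polysubstance users to be somewhat more variable".
- The next sentence gives the size and the power: "Given the power considerations, we increased our sample size to 35 per group, which will give us 90% power to detect fMRI signal changes evoked". The target is restated as "n = 70; 35/condition".
- It closes by saying that, with up to 20% attrition, power is adequate. No figure is attached.

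Three other sections bear on this. Section 5.5 plans for 56 of 70 participants to complete. Section 9.3 restricts the analysis to participants who finished all 10 sessions and have complete primary-endpoint data. Section 9.4.2 tests the time-by-group interaction in a repeated-measures ANOVA ("Results will be presented as F values for the interaction effect, along with p values to indicate statistical significance") and deletes cases with missing data.

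The documents do not give alpha or sidedness for the power calculation, the sample size before the increase, a raw SD, the amount of extra variability, or the pre/post correlation.

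**The concern.** The second remark on variability opens with a contrast, comes after d has been fixed at 0.80, and is followed at once by the increase to 35 per group. The natural reading is that the increase answers the remark and that 90% is what remains afterwards. If the 90% is simply the power at d = 0.80 with everyone evaluable, a more variable population or the expected dropout takes power below the printed figure.

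This affects how the result is read. Section 9.4.1 describes this phase as a first look at intervention effects before full-scale trials. A null result judged against 90% power would count more heavily against an effect than the design supports.

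**Working it through.** **Inputs from the documents.** d = 0.80 between arms, 35 per group, 90% power, prior d = 0.90 (all section 9.2); 56 completers of 70, so 28 per group if dropout is equal (section 5.5); completers-only analysis set (section 9.3).

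**Assumptions, because the documents are silent.** Two-sided 5%, equal arms, a single two-sample comparison without multiplicity correction, and d on the scale of the tested contrast.

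**Formula.** With n evaluable per group, df = 2n − 2 and noncentrality = d × √(n/2). Power is the probability that a noncentral t exceeds the two-sided 5% critical value.

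**Step 1: reproduce the 90%.** For n = 35 and d = 0.80, noncentrality = 0.80 × √17.5 = 3.347, df = 68, critical value 1.995, and power = 91.0% (91.7% by the normal approximation). The printed figure is reproduced. A paired calculation with n = 35 and d = 0.80 gives 99.6%, so it is not the source.

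**Step 2: how much margin is in 35?** At d = 0.80, 34 per group gives 90.2%, so 35 is one person per group above the minimum. With 35 per group, 90% holds down to d = 0.786. Since 0.80 / 0.786 = 1.018, this tolerates an SD about 1.8% larger.

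**Step 3: which allowance is in the number?** At d = 0.90, 90% power needs 27 per group; at d = 0.80 it needs 34. The reduction in d, equivalent to an SD ratio of 0.90 / 0.80 = 1.125, therefore accounts for 7 per group and is included. Any further variability has only the margin in step 2.

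**Step 4: attrition.** 70 × 0.80 = 56, or 28 per group. Noncentrality = 0.80 × √14 = 2.993, df = 54, critical value 2.005, and power = 83.6%, with no further variability.

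**Step 5: illustrative further variability.** If the SD is k times larger, d becomes 0.80 / k.

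| SD | d | Power, 35 per group | Power, 28 per group |
|---|---|---|---|
| as in d = 0.80 | 0.800 | 91.0% | 83.6% |
| +5% | 0.762 | 88.1% | 79.9% |
| +10% | 0.727 | 85.1% | 76.2% |
| +20% | 0.667 | 78.5% | 68.8% |

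Power of 80% is retained down to d of about 0.68 with 35 per group and about 0.76 with 28.

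**Step 6: sensitivity to the assumptions.**

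- *Sidedness.* A one-sided 5% test with 35 per group gives 95.2% at d = 0.80 and holds 90% up to an SD about 13% larger. With 28 per group it gives 90.5% and tolerates about 1%.
- *Scale of d.* If 0.80 is on the post-score SD and the test is on change, the effective d is 0.80 / √(2(1 − ρ)), where ρ is the pre/post correlation. With 35 per group, power is 79.6% at ρ = 0.3, 91.0% at 0.5, 95.8% at 0.6 and 98.9% at 0.7. With 28 per group it is 70.0%, 83.6%, 90.8% and 96.7%.

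**The case against.** The strongest reply is that variability has been allowed for. The move from 0.90 to 0.80 is made expressly for this population and raises the 90% requirement from 27 to 34 per group. Measured from d = 0.90, 35 per group holds 90% up to an SD about 14.5% larger. The two remarks on variability could be one concern stated twice, and the text attributes the increase to power considerations without saying that it was made because of the second remark. This stands. A reader might infer that 90% contains no variability allowance at all, or that the plan claims a specific second allowance and then omits it. The documents support neither: the first allowance is in the number, and the link between the second remark and the increase is implied by order only.

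It can also be said that 35 per group does buy protection if the starting point was the 80%-power size at d = 0.80, which is 26 per group. With 35, power is still about 80% if the SD is about 18% larger (0.80 / 0.679 = 1.178). This also stands, but what is protected is 80% power, not the printed 90%.

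Finally, the tolerance depends on choices the plan leaves open. A one-sided test, or a pre/post correlation above 0.5 with d on the post-score SD, would leave real room at 35 per group; a correlation of 0.3 would leave power below 80%. So it cannot be said categorically that 35 per group is unable to absorb a larger SD at 90% power. Two points weigh against relying on the favourable cases. The hypothesis in section 9.1 is stated against a null of no difference and the planned result is an F test, which does not suggest a one-sided test. And the plan states no correlation.

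**Conclusion.** The point holds in a limited form. Under the stated assumptions, the 90% in section 9.2 is the power for d = 0.80 with all 70 participants evaluable (91.0%). It includes the reduction from 0.90 to 0.80 and nothing further of consequence: about 1.8% in SD at 90% power. Placing the figure directly after the remark about greater variability implies a cover that is not there.

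The better-documented gap is attrition. On the plan's own completion rate and analysis set, power at d = 0.80 is about 84%. The loss from further variability is illustrative, because the plan does not say how much it expects: an SD 10–20% larger gives about 85–79% with 35 per group and 76–69% with 28. These figures could move either way once alpha, sidedness and the pre/post correlation are stated. None of this shows that the trial is too small to proceed. It shows that the stated power needs its conditions attached.

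**What to change.** Keep N = 70 and revise section 9.2.

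1. State alpha, sidedness and the scale on which d = 0.80 is defined, including the pre/post correlation assumed for the time-by-group test. State the sample size before the increase.
2. If the assumptions used here are confirmed, say that 35 evaluable per group gives about 91% power at d = 0.80, with no allowance for variability beyond that d, and that the planned 28 completers per group give about 84%.
3. Add an illustrative range, labelled as such: an SD 10–20% larger gives about 85–79% with 35 per group and about 76–69% with 28. Power of 80% is retained down to d of about 0.68 and 0.76 respectively.
4. Remove the implication that 90% already covers further variability.
5. Put the 28-per-group figures, not the 35-per-group ones, in the closing sentence on attrition.

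If the confirmed assumptions differ, the same statements should be made with recalculated figures. The cost is a few sentences and a less favourable stated power; no participants are added and conduct does not change.

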#### 4.4 END-OF-STUDY DEFINITION

A participant is considered to have completed the study if he or she has completed the baseline assessment, 10 intervention sessions, and post-intervention assessment.

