## 5.5 STRATEGIES FOR RECRUITMENT AND RETENTION

*We anticipate to enroll 70 participants (males and females) who are at least 18 years old across different race and ethnicity based on local demographic characteristics. Subjects will be recruited through print and media ads within local community. This will include radio and online ads and recruitment through social media. Flyers will be distributed throughout the local community. Based on our and other's previous experiences in longitudinal studies, about 5-10% of participants will dropout over the study period due to illness or relocation. We plan a dropout rate of 20% for this brief intervention given the population is polysubstance users. We propose to recruit 70 adults of which 56 (80%) will complete the study.*

*Compensation and Retention. Participants will be financially compensated with \$300 in total for completing the study protocol (approximately for 15 hours of time); participants who only partially complete the protocol will be compensated based on prorated hours. To maximize participant retention we will maintain contact with participants over time via frequent assessment intervals (e.g., requiring a functioning phone number and email address to contact participants by phone or email as needed, and obtaining the name, address, and phone number of at least 2 friends or classmates who can provide contact information for the participants, should we be unable to contact them during the study; emails and reminder phone calls prior to all study visits; offer flexible scheduling options for assessment (including weekends); provide fair compensation to participants; and maintain positive relations with participants. These procedures were used to maintain adequate participant retention in our prior NIH studies.*

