### 7.2 PARTICIPANT DISCONTINUATION/WITHDRAWAL FROM THE STUDY

Participants are free to withdraw from participation in the study at any time upon request.

An investigator may discontinue a participant from the study for the following reasons:

- Significant study intervention non-compliance, unless varying compliance is an aspect of the study objectives
- Lost-to-follow up; unable to contact subject (see **Section 7.3, Lost to Follow-Up**)
- Any event or medical condition or situation occurs such that continued collection of follow-up study data would not be in the best interest of the participant or might require an additional treatment that would confound the interpretation of the study
- The participant meets an exclusion criterion (either newly developed or not previously recognized) that precludes further study participation

The reason for participant discontinuation or withdrawal from the study will be recorded. Subjects who sign the informed consent form and are randomized but do not receive the study intervention may be replaced. Subjects who sign the informed consent form, and are randomized and receive the study intervention, and subsequently withdraw, or are discontinued from the study, will not be replaced.

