#### 9.3 POPULATIONS FOR ANALYSES

*The analysis population will be Modified Intention-to-Treat Analysis Population. Specifically, these participants are those who completed the full-dose of the intervention (10 sessions) and have completed data for the primary endpoint.*

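### The 90% power in section 9.2 belongs to the 35 per group enrolled; at the roughly 28 per arm the plan expects to analyse, the calculation that reproduces it gives about 84%

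*Combined protocol and SAP*

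**What the plan says.** Section 9.2 gives a single power figure: "we increased our sample size to 35 per group, which will give us 90% power to detect fMRI signal changes evoked by IBMT". The same paragraph identifies 35 per condition, 70 in all, as the target sample size. It takes d = 0.80 as the expected effect. It then anticipates up to 20% attrition and calls the power adequate, without a number.

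Four other sections determine how many participants reach the analysis:

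- Section 5.5: "We propose to recruit 70 adults of which 56 (80%) will complete the study". It also reports from experience that "about 5-10% of participants will dropout over the study period due to illness or relocation".
- Section 4.4: "A participant is considered to have completed the study if he or she has completed the baseline assessment, 10 intervention sessions, and post-intervention assessment".
- Section 9.3, on the analysis population: "these participants are those who completed the full-dose of the intervention (10 sessions) and have completed data for the primary endpoint".
- Section 9.4.2: "Missing data will be handled with case-wise deletion".

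Section 7.2 allows limited replacement: "Subjects who sign the informed consent form and are randomized but do not receive the study intervention may be replaced". Anyone who has received the intervention and then leaves is not replaced.

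Section 9.4.2 tests the time-by-group interaction in a repeated-measures ANOVA of voxelwise resting-state data, reported as F values. It adds that "Threshold-free cluster enhancement approach will be used to identify clusters showing significant effects" and that FDR correction is applied.

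**The concern.** A power figure is useful when it describes the analysis that will be done. Here the only figure is tied to the number enrolled, while the plan itself expects a fifth of those people to be absent from the primary analysis. Nothing in the plan brings them back: there is no imputation and no analysis of everyone randomised. A reader who carries the 90% over to the primary analysis would put the chance of missing a true effect of 0.80 at 10%, when the same calculation at the planned analysis size puts it at about 16%. Section 9.4.1 presents this phase as the step before full-scale trials, so the figure should describe the right set.

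**Working it through.** **Inputs from the plan.** Enrolled: 35 per arm (9.2). Planned loss: 20% (5.5, 9.2), so 70 × 0.80 = 56 analysed, about 28 per arm. Effect: d = 0.80 (9.2).

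**Inputs assumed.** Alpha 0.05, two-sided, because 9.2 states neither; two-sided fits the planned interaction F test. d = 0.80 is taken on the between-arm change scale. Section 9.2 frames its aim as a between-arm difference in within-person change, but also places the 0.80 at post-intervention, so the scale is an assumption too.

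**Formula.** With two arms and two time points, the interaction test is a two-sample comparison of change scores. With n per arm, the noncentrality is d × √(n/2) on 2n − 2 degrees of freedom. The normal approximation to power is Φ(d × √(n/2) − 1.96).

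**Step 1: reproduce the stated figure.** At n = 35 the noncentrality is 0.80 × √17.5 = 3.347. Power is 91.0% (noncentral t, 68 df), or Φ(1.387) = 91.7% (normal). Both agree with the stated 90%.

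**Step 2: same calculation at the analysed number.** At n = 28 the noncentrality is 0.80 × √14 = 2.993. Power is 83.6% (noncentral t, 54 df), or Φ(1.033) = 84.9% (normal). Removing two degrees of freedom for the age and sex covariates leaves it at 83.6%.

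**Step 3: between the two.**

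| Analysed per arm | Power (noncentral t) |
|---|---|
| 35 | 91.0% |
| 34 | 90.2% |
| 33 | 89.3% (90.1% normal) |
| 32 | 88.3% |
| 31 | 87.3% |
| 30 | 86.1% |
| 29 | 84.9% |
| 28 | 83.6% |

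The smallest arm size reaching 90% is 34 by the t calculation and 33 by the normal approximation. These correspond to losses of 2/70 = 2.9% and 4/70 = 5.7%. A loss of 5–10% leaves 63 to 66 of 70, about 31 to 33 per arm, with power of about 87–90%.

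**Step 4: detectable effect and imbalance.** At 28 per arm, 90% power needs d = 0.88 and 80% needs d = 0.76. If the 56 split unevenly, power is 82.9% at 24 against 32 and 81.2% at 21 against 35.

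**Step 5: sensitivity to the unstated scale.** If 0.80 is in post-score SD units with equal variances, the change-scale effect is 0.80/√(2(1 − r)), where r is the pre-post correlation. At 28 per arm:

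| Assumed r | Change-scale d | Power |
|---|---|---|
| 0.3 | 0.676 | 70% |
| 0.5 | 0.800 | 84% |
| 0.6 | 0.894 | 91% |
| 0.7 | 1.033 | 97% |

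**Step 6: inputs that would give 90% at 28 per arm.** One-sided 5% gives 90.5%. A correlation of 0.589 on the post-score reading gives 90.0%. A two-sided test at d = 0.90 gives 91.1%. At 35 per arm the same inputs give 95.2%, 95.3% and 96.0%, so none of them reproduces the sentence as written.

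**The case against.** The strongest defence is that nothing in 9.2 is false. Thirty-five per group does give about 90%, and the attrition sentence claims only adequate power, which 84% satisfies by the usual 80% yardstick. That stands, and it limits the point: the stated figure was not miscalculated. It does not remove the point, because the attrition sentence has no number and the one number given is for a set the plan does not expect to analyse.

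A second defence is that 28/0.80 = 35 exactly, and 9.2 speaks of an increase to 35, so 90% may have been computed for 28 and then inflated. The hypothesis in 9.1 is also directional. This is possible, and the inputs in Step 6 would do it. But the text attaches 90% to 35, adopts 0.80 rather than 0.90, gives no correlation, and plans an F test, which is not one-sided. On this reading the sentence still needs correcting.

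A third is replacement under 7.2. It is optional and does not cover anyone who started the intervention. Reaching 29 or 30 per arm would give about 85% or 86%.

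Stronger readings are tempting, and the documents do not support them:

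- *The trial is underpowered or must enrol more.* On the main reading power stays above 80%, even with the uneven splits shown.
- *The 90% already fails at the 5–10% loss seen in experience.* This depends on the approximation. The normal calculation still gives 90.1% at 33 per arm, and the shortfall by the t calculation is only about 1 to 3 points.
- *A null result could not be interpreted.* It would be read from the estimate and its precision, and 9.4.1 plans effect sizes.
- *The 0.80, or the 9.4.1 remark about smaller effects, is wrong.* The basis for 0.80 lies in cited work not available here, and whether the 9.4.1 remark holds depends on the unstated correlation. No error is shown in either.

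**Conclusion.** The point holds as a mismatch between the stated power and the planned analysis set. On the reading that reproduces the 90%, power at the expected 28 per arm is about 84% (85% by the normal approximation), some 6 points below the stated figure. This rests on three assumptions: a two-sided 5% test, d = 0.80 on the change scale, and the planned 20% loss falling about equally on the arms. The first two cannot be confirmed from the text; if 0.80 is on the post-score scale, correlations of 0.3 to 0.7 give 70% to 97%. Confidence in the exact replacement figure is therefore moderate. That 90% is attached to the enrolled rather than the analysed number is plain from the text.

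Neither 90% nor 84% is the power of the whole-brain TFCE and FDR-corrected test in 9.4.2. Both describe a single summary measure of ACC/mPFC activity.

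**What to change.** Reword 9.2 to give power at the analysed number. For example: *70 recruited, about 56 analysed (28 per arm); power about 84% for a between-arm d of 0.80 in change on a single ACC/mPFC summary measure, two-sided 5%; 90% needs d = 0.88.* State the alpha, sidedness, scale of d and pre-post correlation actually used, and replace the 84% if they lead to a different figure. If the sponsor's own inputs give 90% at 28 per arm, attach the 90% to 28 analysed and show those inputs. Add a sentence saying that the figure is not the power of the whole-brain corrected test in 9.4.2.

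The cost is a change of wording. Enrolment, endpoint and analysis stay as they are. The stated figure becomes somewhat less favourable unless the sponsor's inputs support a higher one.
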